## **FORESEEABLE RISKS AND DISCOMFORTS**

Provide a brief description of any foreseeable risks and discomforts to subjects. Include those related to drugs/devices/procedures being studied and/or administered/Performed solely for research purposes. In addition, include psychosocial risks, and risks related to privacy and confidentiality. When applicable, describe risks to a developing fetus or nursing infant.

As described above, all patients will be treated with the standard of care and should therefore not be exposed to any additional risk or discomfort. As is typical practice, all patients will receive an intravenous (IV) line and baseline labs on admission to the L&D floor, and oxytocin will be given immediately after the baby is delivered and the cord clamped. Thereafter, patients will receive all usual measures to manage postpartum bleeding, including, but not limited to, administration of additional uterotronics, uterine massage, additional diagnostic lab values and resuscitative measures. Second-line uterotronics will be given as per study protocol, with additional uterotronics as per clinical assessment.

After the delivery, the patient will be monitored on the labor and delivery floor for several hours postoperatively before discharge to the postpartum recovery unit, as is customary.

Only clinical providers will be involved in the care of the patient. Study staff will be involved in consent and collection of data points during enrollment, but they will not participate directly in patient care. Privacy and confidentiality will be maintained as per HIPAA standards.

## **EXPECTED BENEFITS**

Describe both the expected benefits to individual subjects participating in the research and the importance of the knowledge that may reasonably be expected to result from the study. Provide a brief, realistic summary of potential benefits to subjects, for example, "It is hoped that the treatment will result in a partial reduction in tumor size in at least 25% of the enrolled subjects." Indicate how the results of the study will benefit future patients with the disease/condition being studied and/or society, e.g., through increased knowledge of human physiology or behavior, improved safety, or technological advances.

The incidence of PPH is on the rise in the U.S.A., with uterine atony the main etiology. Oxytocin is given prophylactically in cesarean section deliveries, but when it is inadequate, second-line agents are required. While recent literature suggests methylergonovine may be more effective than carboprost for PPH treatment, no prospective data exists comparing the two. This study may yield new information demonstrating the comparative efficacy of these two drugs. This could guide future practice in determining which second-line agent is preferred for PPH management. In turn, this could allow future

patients to benefit from decreased morbidity and mortality associated with hemorrhage and transfusion.

### **EQUITABLE SELECTION OF SUBJECTS**

The risks and benefits of the research must be fairly distributed among the populations that stand to benefit from it. No group of persons, for example, men, women, pregnant women, children, and minorities, should be categorically excluded from the research without a good scientific or ethical reason to do so. Please provide the basis for concluding that the study population is representative of the population that stands to potentially benefit from this research.

All English-speaking patients undergoing non-emergent urgent C/S at the Brigham and Women's Hospital and all English or non-English speaking patients undergoing scheduled C/S will be eligible for participation except those with a known coagulopathy or high risk for coagulopathy (as this might alter the management of bleeding beyond standard measures) as well as those with contraindications to either study drug, i.e. HTN or active asthma (with use of a bronchodilator in the past 24 months) or documented allergy to either drug. Patients refusing to receive blood products due to religious beliefs will also be excluded.

Patients experiencing uterine atony requiring an additional, second-line uterotonic agent after C/S will be randomized to participate in this study, as a result, those who participate will be of the same population that will benefit from this research.

When people who do not speak English are excluded from participation in the research, provide the scientific rationale for doing so. Individuals who do not speak English should not be denied participation in research simply because it is inconvenient to translate the consent form in different languages and to have an interpreter present.

Non-English speaking patients who are undergoing unscheduled, urgent C/S will not be enrolled due to the potentially stressful or urgent nature of all C/S in patients who have failed to deliver in labor. In such cases, there may not be time to adequately obtain informed consent for participation in the study without hindering clinical care. Therefore the study will only enroll urgent C/S patients who speak English and are able to provide informed consent without the aid of an interpreter. Patients undergoing routine, schedule C/S may be English-speaking or non-English speaking, since there will be no undue stress involved preoperatively and there will be ample opportunity for full consent in the patient's first language with the aid of an official in-person interpreter.

For guidance, refer to the following Partners policy:

## RECRUITMENT PROCEDURES

Explain in detail the specific methodology that will be used to recruit subjects. Specifically address how, when, where and by whom subjects will be identified and approached about participation. Include any specific recruitment methods used to enhance recruitment of women and minorities.

Eligible patients undergoing a scheduled C/S or non-emergent C/S after labor will be provided with the study Flier regarding the study and the study consent form by a study physician investigator or research assistant when they are admitted to the L&D floor. The person will not be directly involved in the care of the patient. Patients will only be approached in their rooms by a study physician to obtain their informed consent. The study physician will follow all institutional policies and contact isolation level safety procedures to minimize risks to the patient of possible COVID-19 exposure. They will maintain a 6-foot distance from the patient as much as possible. There will be minimal shared points of contact between study staff and patient, (such as the consent form, clipboard, or pen). Proper hand hygiene and replacement of PPE will be performed throughout as necessary.

At this time, patients will have the opportunity to ask any questions they may have regarding the study and to opt in or out as desired through conversation with the physician study investigator. During this conversation, the purpose of the study and scope of participation will be discussed. If the patient is agreeable to participation, written consent will be obtained by the physician study investigator. If the patient is non-English speaking, the services of an in-person interpreter will be obtained for the conversation with the study investigator.

Provide details of remuneration, when applicable. Even when subjects may derive medical benefit from participation, it is often the case that extra hospital visits, meals at the hospital, parking fees or other inconveniences will result in additional out-of-pocket expenses related to study participation. Investigators may wish to consider providing reimbursement for such expenses when funding is available

No remuneration will be provided for participation in this study.

For guidance, refer to the following Partners policies:  
Recruitment of Research Subjects

[https://partnershealthcare-public.sharepoint.com/ClinicalResearch/Recruitment Of Research Subjects.pdf](https://partnershealthcare-public.sharepoint.com/ClinicalResearch/Recruitment%20Of%20Research%20Subjects.pdf)

Guidelines for Advertisements for Recruiting Subjects

[https://partnershealthcare-public.sharepoint.com/ClinicalResearch/Guidelines For Advertisements.1.11.pdf](https://partnershealthcare-public.sharepoint.com/ClinicalResearch/Guidelines%20For%20Advertisements.1.11.pdf)

Remuneration for Research Subjects

[https://partnershealthcare-public.sharepoint.com/ClinicalResearch/Remuneration for Research Subjects.pdf](https://partnershealthcare-public.sharepoint.com/ClinicalResearch/Remuneration%20for%20Research%20Subjects.pdf)

## CONSENT PROCEDURES

Explain in detail how, when, where, and by whom consent is obtained, and the timing of consent (i.e., how long subjects will be given to consider participation). For most studies involving more than minimal risk and all studies involving investigational drugs/devices, a licensed physician investigator must obtain informed consent. When subjects are to be enrolled from among the investigators' own patients, describe how the potential for coercion will be avoided.

All pregnant women receiving care from participating obstetricians will receive an initial informational study Flier and consent form in their 28-wk prenatal information package from the obstetrician's office.

Upon admission to the L&D unit, all potentially eligible patients will be pre-screened using the OB Pre-Screen Questionnaire for 2nd Line Uterotonics Study. Those who meet eligibility criteria will, once again, receive the study Flier and consent form. A physician study investigator who is not involved in their care at the time of consent will review and discuss the study plan at this time, allowing subjects the opportunity to ask questions and address any of their concerns or any issues surrounding the study. Subjects interested in participating will then be consented by the physician investigator and enrolled in the study. An official in-person interpreter fluent in the patient's native language will be used to translate an oral version of the English consent form in the patient's native language. Social distancing will be maintained during all in-person conversations and appropriate PPE will be worn by any staff during these conversations. The patient will be allowed to keep the pen they use to sign the consent form, in order to minimize sharing of physical items, and lower the risk for COVID-19 transmission.

NOTE: When subjects are unable to give consent due to age (minors) or impaired decision-making capacity, complete the forms for Research Involving Children as Subjects of Research and/or Research Involving Individuals with Impaired Decision-making Capacity, available on the New Submissions page on the PHRC website:

<https://partnershealthcare.sharepoint.com/sites/phrmApply/aieipa/irb>

For guidance, refer to the following Partners policy:

Informed Consent of Research Subjects:

[https://partnershealthcare-public.sharepoint.com/ClinicalResearch/Informed\\_Consent\\_of\\_Research\\_Subjects.pdf](https://partnershealthcare-public.sharepoint.com/ClinicalResearch/Informed_Consent_of_Research_Subjects.pdf)

## DATA AND SAFETY MONITORING

Describe the plan for monitoring the data to ensure the safety of subjects. The plan should include a brief description of (1) the safety and/or efficacy data that will be reviewed; (2) the planned frequency of review; and (3) who will be responsible for this review and for determining whether the research should be altered or stopped. Include a brief description of any stopping rules for the study, when appropriate. Depending upon the risk, size and complexity of the study, the investigator, an expert group, an independent Data and Safety Monitoring Board (DSMB) or others might be assigned primary responsibility for this monitoring activity.

NOTE: Regardless of data and safety monitoring plans by the sponsor or others, the principal investigator is ultimately responsible for protecting the rights, safety, and welfare of subjects under his/her care.

The principal investigator will be responsible for reviewing the study data after each 5th enrolled patient. The purpose of these reviews will be to identify and correct any potentially unsafe practice or result occurring among the study population. This includes specifically any delay in uterotonic administration, lack of an appropriate uterotonic being administered, or the use of a uterotonic in a patient with a contraindication to that drug.

Any adverse events identified by the principal investigator, or any of the other study investigators, will be reported to the PHRC in accordance with the PHRC Policy on Unanticipated Problems Involving Risks to Subjects or Others, including Adverse Events.

Describe the plan to be followed by the Principal Investigator/study staff for review of adverse events experienced by subjects under his/her care, and when applicable, for review of sponsor safety reports and DSMB reports. Describe the plan for reporting adverse events to the sponsor and the Partners' IRB and, when applicable, for submitting sponsor safety reports and DSMB reports to the Partners' IRBs. When the investigator is also the sponsor of the IND/IDE, include the plan for reporting of adverse events to the FDA and, when applicable, to investigators at other sites.

NOTE: In addition to the adverse event reporting requirements of the sponsor, the principal investigator must follow the Partners Human Research Committee guidelines for Adverse Event Reporting

Upon review at the end of each of 5 patients recruited, the principal investigator will note specific frequency of minor and serious adverse events experienced by subjects. Any incidence of frequent minor events or any single serious adverse event will trigger a report generated for submission to the Partners IRB. For any serious concern, the Principal Investigator will halt the study until further discussion with the IRB.

## MONITORING AND QUALITY ASSURANCE

Describe the plan to be followed by the principal investigator/study staff to monitor and assure the validity and integrity of the data and adherence to the IRB-approved protocol. Specify who will be responsible for monitoring, and the planned frequency of monitoring. For example, specify who will review the accuracy and completeness of case report form entries, source documents, and informed consent.

NOTE: Regardless of monitoring plans by the sponsor or others, the principal investigator is ultimately responsible for ensuring that the study is conducted at his/her investigative site in accordance with the IRB-approved protocol, and applicable regulations and requirements of the IRB.

All physician co-investigators involved in this study will be well informed of recruitment procedures, location of study medications storage, appropriate handling of medications and timing of administration, as well as other protocol details.

The principal investigator will conduct a review of source documentation after every 5 enrolled patients, weekly, or immediately upon recognition of any adverse event. The principal investigator will ensure that the study protocol is conducted in accordance to the final approved IRB. This includes ensuring that recruited patients meet eligibility criteria and are provided with study information in advance of enrollment; reviewing consent documentation and reviewing collected data to ensure that all items are completed, including complications and potential adverse events, and that the data is free of patient identifiers; and following-up on any reported concerns from patients, study staff, or clinicians.

For guidance, refer to the following Partners policies:

Data and Safety Monitoring Plans and Quality Assurance

[https://partnershealthcare-public.sharepoint.com/ClinicalResearch/DSMP\\_in\\_Human\\_Subjects\\_Research.pdf](https://partnershealthcare-public.sharepoint.com/ClinicalResearch/DSMP_in_Human_Subjects_Research.pdf)

Reporting Unanticipated Problems (including Adverse Events)

[https://partnershealthcare-public.sharepoint.com/ClinicalResearch/Reporting\\_Unanticipated\\_Problems\\_including\\_Adverse\\_Events.pdf](https://partnershealthcare-public.sharepoint.com/ClinicalResearch/Reporting_Unanticipated_Problems_including_Adverse_Events.pdf)

## **PRIVACY AND CONFIDENTIALITY**

Describe methods used to protect the privacy of subjects and maintain confidentiality of data collected. This typically includes such practices as substituting codes for names and/or medical record numbers; removing face sheets or other identifiers from completed surveys/questionnaires; proper disposal of printed computer data; limited access to study data; use of password-protected computer databases; training for research staff on the importance of confidentiality of data, and storing research records in a secure location.

NOTE: Additional measures, such as obtaining a Certificate of Confidentiality, should be considered and are strongly encouraged when the research involves the collection of sensitive data, such as sexual, criminal or illegal behaviors.

All data related to this study will be treated as confidential. Email communication to potential subjects at term gestation will be sent securely, in accordance with MGB Information Security guidelines. Collected data will be consolidated and entered directly in a de-identified fashion into a secure electronic capture tool, REDCap. Patient MRNs will be the only patient identifier recorded in REDCap; these will be entered with study group allocation and study ID number separately from the other study data into a secure document on REDCap by the unblinded principal investigator. The MRNs will be linked to study information on the randomization sheets, which will be viewed only by the unblinded principal investigator and stored in a locked filing cabinet in a locked office, accessible only by the principal investigator. Any other paper documentation related to study patients and containing patient identifiers will be maintained in the same locked filing cabinet, accessible only by the principal investigator.

Only the principal investigator, and one unblinded co-investigator will have access to the REDCap files. No one other than the study investigators will have any knowledge of the details of the patient's study information, and this data will never be circulated electronically or in any other format.

## **SENDING SPECIMENS/DATA TO RESEARCH COLLABORATORS OUTSIDE PARTNERS**

Specimens or data collected by Partners investigators will be sent to research collaborators outside Partners, indicate to whom specimens/data will be sent, what information will be sent, and whether the specimens/data will contain identifiers that could be used by the outside collaborators to link the specimens/data to individual subjects.

No specimens or data will be collected or sent to research collaborators outside Partners or participating sites.

Specifically address whether specimens/data will be stored at collaborating sites outside Partners for future use not described in the protocol. Include whether subjects can withdraw their specimens/data, and how they would do so. When appropriate, submit documentation of IRB approval from the recipient institution.

Not applicable to this study.

Second-Line Uterotonics in Postpartum Hemorrhage: A Randomized Clinical Trial

NCT: 03584854

April 04, 2018

*Biostatistical Analysis Plan*

An a priori power analysis determined that enrollment of 37 patients per group would provide 80% power at a 2-sided alpha level of 0.05 to detect a 1-point difference, with estimated within-group standard deviation of 1.5, in mean uterine tone at 10 minutes after study drug administration using a two-sample t-test. Randomization of 100 patients was planned to account for protocol violations. Uterine tone at 10 minutes (primary outcome) and 5 minutes (secondary outcome) after study drug administration were compared between groups with adjustment for baseline tone and trial site using the generalized estimating equations (GEE) method with an identity link to account for the correlation between repeated measurements on the same patient. The primary analysis was a complete-case analysis, where 3 patients (3%) missing uterine tone at baseline and/or 10 minutes were excluded from the analysis. A multiple imputation sensitivity analysis was also performed which used the multivariate imputation by chained equations approach to impute missing uterine tone values using observed tone measurements (baseline, 5, and 10 minutes), parturient characteristics (age, race, BMI, parity), infant characteristics (number of fetuses, infant birth weight), trial site, interventions (randomized study drug, administration of second study drug, intraoperative transfusion), and outcomes (intraoperative blood loss, change in hematocrit from baseline to 24 hours post-delivery) to create 10 complete datasets. The primary outcome was compared in each of the 10 imputed datasets, and results combined using Rubin's rule.

All continuous secondary outcomes were initially assessed for the normality of residuals from a multivariable linear regression model with trial site and baseline uterine tone as covariates. Outcomes displaying normally distributed model residuals were analyzed using multivariable linear regression, with effect size presented as adjusted difference in means with 95% CI. Outcomes with all non-zero values that displayed skewed linear regression model residuals were natural log-transformed and analyzed using multivariable linear regression, with effect size presented as adjusted ratio of geometric means with 95% CI. Outcomes containing at least one zero value that presented skewed linear regression model residuals were compared between groups using multivariable quantile regression, with effect size presented as adjusted difference in medians with 95% CI.

All binary outcomes were initially considered for comparison using multivariable logistic regression (for single measurements) or generalized estimating equations with a logit link (for repeated measurements) with trial site and baseline uterine tone as covariates. If the multivariable regression converged, effect size was presented as adjusted odds ratios with 95% CI. If the model did not converge due to low incidence, groups were compared using a Fisher's exact test and effect size presented as risk difference with exact 95% CI.

Time to receive second study drug was compared between groups using a multivariable Cox proportional hazards model, with effect size presented as adjusted hazard ratio with exact 95% CI. Complete-case analysis was performed for all secondary outcomes. All analyses were performed using SAS software version 9.4 (SAS Institute, Cary, NC).

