## **V. STUDY PROCEDURES**

All subjects will have an IV placed and baseline labs sent, as is standard for all patients admitted to the Center for Women and Newborns Labor and Delivery unit. Baseline labs will include: type and screen and complete blood count (CBC).

At the time of delivery, enrolled subjects will be assessed for poor uterine tone despite the administration of oxytocin following delivery. If either methylergonovine or carboprost is requested by the obstetrician or anesthesiologist, subjects will then be randomized by the anesthesiologist to either "methylergonovine" or "carboprost" groups by a computer generated randomization scheme printed on a piece of paper in a sealed envelope. The anesthesiologist will then withdraw the appointed medication (based on subject randomization) from the O.R. omnichannel and administer it without revealing to anyone in the O.R. which drug was given. They will document the medication in the subject's Epic record in the usual fashion.

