At the time of administration of the first study drug, the anesthesiologist will ask the obstetrician to rate the uterine tone on a scale of 0 to 10 (0 being 'no tone', 10 being 'excellent tone'). The anesthesiologist will then set a timer. After administration of the study drug, patient care will receive our usual standard of care. At 5 and 10 minutes from the onset of timing, the anesthesiologist will once again ask the obstetrician for a rating of uterine tone between 0 and 10. These values will be recorded by the anesthesiologist on a Uterine Tone Score Intraop Data Collection sheet included in the sealed envelope provided by the investigator.

If an additional uterotonic agent is requested by the obstetrician, the unblinded anesthesiologist will prepare the other drug, again in a-1mL syringe. Timing of this administration will be noted on the study record sheet. All other medications and interventions will proceed as usual and in an unblinded fashion.; If uterine tone remains unsatisfactory, identity of the study drugs will remain blinded, if possible. Any repeat administrations of carboprost or methylergonovine will be given by the anesthesiologist based on the timing of administration of the 2nd study drug.

The obstetric physicians and nurses caring for the patient will document quantitatively measured blood loss during the delivery. The volume of blood mixed with amniotic fluid in the graduated suction jars and the number of sponges soaked with blood will be noted. In addition to baseline serum hematocrit, postpartum serum hematocrit and platelet count, will be evaluated on the first postoperative day after C/S. The change in serum hematocrit will be compared among study groups.

At the end of the C/S, the anesthesiologist will complete the Randomization Sheet, documenting the patient MRN and study ID number. They will return the Randomization sheet and the Uterine Tone Score Intraop Data Collection sheet in the [previously sealed] envelope to a locked room on L&D where all paper documents for the study will be temporarily stored until the unblinded principal investigator collects the sheets (on the same day as subject enrollment) and brings them to a locked filing cabinet in a locked office to which only the principal investigator has access.

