## VI. BIOSTATISTICAL ANALYSIS

- a. Specific data variables being collected for the study (e.g., data collection sheets).

Baseline patient characteristics will be collected and documented on data collection sheets. These characteristics will include:

1. patient MRN
2. randomization group
3. age
4. height, weight, BMI
5. gravidity and parity
6. baseline hematocrit and platelet count measured at the time of admission or on the day of delivery

- b. Statistical methods

The balance of patient characteristics between the two groups before intervention will be evaluated using standardized differences. Shapiro-Wilk test will be used to confirm whether the primary endpoint, uterine tone score 10 minutes after drug administration, satisfies the normality assumption. Multiple linear regression will be conducted when normality assumption satisfied. In the case when the normality assumption is not established, log transformation/box-cox transformation of the outcome will be carried out before modeling. For secondary endpoints that are dichotomous, logistic regression will be used to

examine the intervention effect after adjusting for potential confounders. For continuous secondary endpoints, such as intrapartum blood loss, we will evaluate its distribution before performing appropriate modeling. Trial site will be included as a covariate in all models to adjust for the stratification of randomization by hospital.

c. Power analysis (e.g., sample size, evaluable subjects, etc.)

Assuming a common within-group standard deviation in uterine tone score of 1.9 points, a minimum sample size of 41 randomized patients per group would provide 80% power at a two-sided alpha level of 0.05 to detect a 1.2 point difference in mean uterine tone score at 10 minutes post secondary uterotonic administration between groups using a two-sample t-test. A total of 50 patients per group (100 patients total) will need to be randomized to account for protocol violations. Since we currently perform 175 C/S monthly at BWH, and approximately 20 patients undergoing non-emergent C/S receive methergine or hemabate for uterine atony each month, we anticipate needing to enroll 1250 patients in total to be able to randomize 100 patients to receive the study intervention.

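### Hematocrit change should be adjusted for the pre-delivery value already collected; two smaller wording gaps in the SAP's secondary-outcome rules should also be closed

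*SAP*

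**What the plan says.** The SAP sorts secondary outcomes by type. Continuous ones were first "assessed for the normality of residuals from a multivariable linear regression model with trial site and baseline uterine tone as covariates". Three rules follow:

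- Normal residuals: linear regression.
- Skewed residuals, no zeros: "Outcomes with all non-zero values that displayed skewed linear regression model residuals were natural log-transformed and analyzed using multivariable linear regression".
- Skewed residuals, some zeros: "Outcomes containing at least one zero value that presented skewed linear regression model residuals were compared between groups using multivariable quantile regression", reported as an adjusted difference in medians.

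Binary outcomes go to logistic regression or GEE, with Fisher's exact test as fallback. On missing data: "Complete-case analysis was performed for all secondary outcomes".

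The SAP mentions hematocrit only among the imputation variables, as "change in hematocrit from baseline to 24 hours post-delivery". Protocol section V says: "The change in serum hematocrit will be compared among study groups". The pre-delivery value appears there as part of a baseline blood count for all subjects, in section VI as "baseline hematocrit and platelet count measured at the time of admission or on the day of delivery", and as a preoperative hematocrit column on the data collection sheet. The analyte varies. Section V (Study Procedures text), item 6 of the Protocol Summary's secondary endpoints and the SAP say hematocrit. Section II item f and item 6 of the detailed protocol's secondary endpoints say hemoglobin.

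Units of blood product given within 24 hours of delivery is a listed secondary outcome in section II item c and item 3 of both endpoint lists. The SAP does not mention it. Protocol section VI promises site as a covariate in all models and leaves the model for continuous secondary endpoints open until the distribution has been seen.

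**The concern.** The primary outcome is an obstetrician's 0 to 10 rating. Hematocrit change and transfusion are among the objective measures that help a reader interpret it, so their analyses should be clear and reasonably precise.

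**(a) Main point.** A change score still depends on where the patient started. The SAP adjusts uterine tone for its own baseline, but adjusts hematocrit change for baseline tone and not for baseline hematocrit. The interval may be wider than it needs to be, and a chance imbalance in starting hematocrit is left uncorrected.

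**(b) Minor correction.** The log rule asks only that no value be zero. Hematocrit change can be negative, and a negative number has no logarithm.

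**(c) Clarification.** Units transfused is a count. The SAP has continuous, binary and time-to-event rules but does not say which applies. One reading leads to a median difference that may carry no information.

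**Working it through.** **Scope.** The SAP's only sample-size figure, 37 per group, concerns the primary outcome. A two-sample t-test with difference 1, SD 1.5 and two-sided alpha 0.05 gives 37 per group (power 0.808), so it reproduces. The protocol's 41 per group (difference 1.2, SD 1.9) also reproduces (power 0.807). Nothing below alters either.

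**(a) Precision for hematocrit change.** Let r be the within-arm pre/post correlation and k the post-delivery SD divided by the pre-delivery SD. Both are assumptions. In units of the pre-delivery variance:

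- residual variance of the change score: 1 + k² − 2rk
- residual variance after adding the pre-delivery value: k²(1 − r²)
- ratio: k²(1 − r²)/(1 + k² − 2rk), which is (1 + r)/2 when k = 1

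Worked case, k = 0.8 and r = 0.5: 0.64 × 0.75/(1 + 0.64 − 0.8) = 0.48/0.84 = 0.571.

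| k | r = 0.5 | r = 0.6 | r = 0.7 | r = 0.8 |
|---|---|---|---|---|
| 0.8 | 0.571 | 0.602 | 0.628 | 0.640 |
| 1.0 | 0.750 | 0.800 | 0.850 | 0.900 |
| 1.2 | 0.871 | 0.922 | 0.966 | 0.997 |

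At k = 1 the confidence interval narrows by 1 − √((1 + r)/2), about 13%, 11%, 8% and 5%. A check with 4,000 simulated trials of 97 patients, with site and tone in both models, gave variance ratios of 0.751, 0.823, 0.847 and 0.911. At n = 97 these gains match the precision of 97/0.75 = 129 patients at r = 0.5, down to 97/0.90 = 108 at r = 0.8. The 97 is illustrative: it is 100 less the three patients excluded for missing tone, and the number with hematocrit data is not stated.

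A patient without a pre-delivery value has no change score and is already out of a complete-case analysis. The covariate therefore removes no one and costs one degree of freedom.

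**(b) Log rule.** By combination:

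- Normal residuals: linear regression, which works with any sign.
- Skewed residuals, at least one exact zero: quantile regression, which works with any sign.
- Skewed residuals, no zero, all values positive: log, which works.
- Skewed residuals, no zero, at least one negative value: log, which is undefined.

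Only the last fails. With assumed normal changes (mean −3 to −5 points, SD 3 to 4, rounded to 0.1, 97 patients), 46% to 73% of simulated trials had mixed signs and no exact zero. Reversing the sign to a drop does not help, since all values were positive in under 1% of trials. This is not a failure rate, because failure also needs skewed residuals and the documents give no evidence on skew.

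**(c) Units transfused.** If units are treated as continuous, zeros and skew lead to the median rule. With 50 per arm and the same assumed transfusion rate in both arms, the probability that both raw medians are 0 is P(at most 24 of 50 transfused)², which is at least 0.995 for rates of 5% to 30% and 0.81 at 40%. With different rates, 600 simulated trials per scenario (1 + Poisson(1.5) units if transfused; median regression on arm, site and tone) gave these shares with an adjusted median difference of exactly 0:

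| Assumed rates | Share at 0 |
|---|---|
| 10% v 20% | 100% |
| 20% v 30% | 99.8% |
| 30% v 40% | 93% |
| 20% v 45% | 79% |
| 20% v 55% | 24% |
| 10% v 60% | 8% |

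The problem fades as one arm nears or passes half transfused. The documents give no transfusion rate.

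**The case against.** The case against giving this much weight is fair in several respects.

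- **The covariate is a matter of precision, not correctness.** Under randomization the change-score comparison is unbiased, and at k = 1.2 and r = 0.8 the variance gain is 0.3%. This stands. What remains is that the covariate is already collected and adding it loses no patient.
- **The covariate list is attached to the residual-screening model.** The final model is described only as multivariable linear regression. Carrying the same covariates forward is the natural reading, but it is an inference. On either reading the pre-delivery value is never named.
- **For outcomes that cannot be negative, non-zero already means positive.** True of blood loss and length of stay. The gap concerns signed outcomes only.
- **The SAP assigns outcomes by type, so not naming units transfused is drafting style.** This largely stands. A reader might infer that the endpoint was dropped or has no analysis. The documents do not support that: read as continuous, it reaches the quantile rule; read as binary, the logistic rule. The transfusion variable in the imputation list does not settle which, since it is intraoperative and the endpoint runs to 24 hours.
- **A yes/no effect size would itself be a compromise.** The protocol defines the endpoint as a number of units. At assumed rates from 5% v 10% to 30% v 40%, the binary rule had 9% to 27% power and a site-stratified rank test 10% to 31%. With 20% transfused in both arms and different quantities, power was 6% and 7%. Statisticians could reasonably differ on replacing the outcome, so it is not required here.

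**Conclusion.** The point holds for secondary outcomes only. Its main part is an improvement that needs no new data: adjust hematocrit change for its pre-delivery value. The variance reduction is 25% to 10% with equal SDs and r of 0.5 to 0.8, and 43% to nearly nil when the SD ratio runs from 0.8 to 1.2. These ranges rest on assumed r and k.

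The log-rule wording is a small, definite correction. It applies only to a signed outcome with skewed residuals, a negative value and no exact zero. A reader might infer that the rule did break down for hematocrit change; nothing in the documents shows that.

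For units transfused, the supportable statement is that the classification is not given, and that the continuous reading is uninformative when clearly fewer than half of each arm is transfused, a rate that has to be assumed.

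Two stronger conclusions are not supported: that the hematocrit comparison is biased or invalid, and that the primary result or sample size is touched.

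**What to change.** In the SAP's paragraph on continuous secondary outcomes:

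- **(a)** For hematocrit change, add the pre-delivery value of the same analyte as a covariate beside trial site and baseline tone, keeping the residual check. State whether the analyte is hematocrit or hemoglobin, and align protocol sections II and V and the Protocol Summary.
- **(b)** Make the condition for log transformation that every value is strictly positive. Send skewed outcomes with any zero or negative value to the existing quantile rule.
- **(c)** State whether units transfused within 24 hours is continuous or binary, and tabulate units by arm whichever is chosen. Optional additions are any transfusion (yes/no) as the effect size, a site-stratified rank test on units, and a rule that omits the median difference when more than half the values are 0 in each arm. The price is no effect size in units in the usual case, and little power.

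The SAP is in the past tense and already reports exclusions, so any rerun should be labelled post hoc and shown beside the existing result.

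Cost: a few sentences of SAP wording and a rerun of at most two secondary outcomes. No new data are needed and (a) loses no patient.
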